6. Contact information for Principal Investigator

7. Notation if requesting exemption from or alteration of written consent documentation and/or waiver of HIPAA authorization

We will obtain consent from therapists and supervisors to participate in the study, and research staff will obtain consent from young adults aged 18-24, as well as assent from youth ages 7-17 and consent from their parents/legal guardians.

We have requested waiver of documentation of parental consent when a youth client 7-17 years presents to their treatment session without a parent/legal guardian. While piloting our procedures at our first agency, we have identified a major barrier to enrollment of these clients. Many youth clients present to the community mental health agencies for their treatment session without a parent/legal guardian, particularly adolescents who can come to session on their own using public transportation. We have discussed potential solutions to this barrier with therapist stakeholders and have learned that a parent/legal guardian can often be reached by phone during the client's session even if they do not accompany youth to session. As such, we have requested waiver of documentation of parental consent when a youth client 7-17 years presents to their treatment session without a parent/legal guardian. Our justification is as follows:

- The research involves no more than minimal risk to the subjects, as we are asking youth clients to agree to the audio recording of their session. The primary risk related to study participation is the breach of confidentiality of the audio recording. We minimize this risk by immediately transferring

the audio recording to an encrypted hard drive.

- The waiver or alteration will not adversely affect the rights and welfare of the subjects, since we will still obtain assent in person from the youth client and consent from the parent/guardian over the phone in the presence of the youth client. The only difference from our currently approved consenting process is that the parent/legal guardian will not be physically present in the room during parental consent and a signed consent form will not be obtained from the parent/legal guardian.
- The research could not practically be carried out without the waiver or alteration, because many youth clients 7-17 years present to their treatment session without a parent/legal guardian. If we do not obtain this waiver of documentation of consent, then we would have to significantly increase the amount of time needed to enroll three clients per therapist, which could be perceived as too burdensome on an agency and could influence agencies and therapists not to participate in this study. Additionally, this research could not practically be carried out without waiver of documentation of parental consent for youth who want to participate but whose parent/legal guardian cannot feasibly attend the session. We want to be able to provide these youth with a fair opportunity to participate if they express interest in participating in this study.

Our process to obtain verbal consent from parents/legal guardians is as follows: when a youth client 7-17 years present to their treatment session without a parent/legal guardian, then the therapist will call the parent/legal guardian and if s/he agrees to hear more about the study, the research team will speak to the parent/legal guardian on the phone in the presence of the therapist and client. If the parent/legal guardian verbally consents to allow their child to participate in the study and the client assents to participate in the study, the research team will obtain signed assent from the youth client and write a note documenting the consenting process of the parent/legal guardian. This note will be maintained with the client's assent form in a locked filing cabinet in a locked office room.

We have requested alteration of documentation of youth, caregiver, and young adult assent/consent when participants cannot sign consent/assent forms in-person (as in the case of the COVID-19 outbreak). Specifically, when a client and/or caregiver is interested in participating in the study, we will obtain verbal assent and/or consent from the client and/or caregiver. Research staff typically meet with clients and caregivers around their scheduled therapy sessions at community mental health agencies to minimize burden to families. However, when it is not possible to meet with clients and caregivers in-person, we will enroll them through a virtual platform. Not allowing eligible clients and caregivers to participate in the study virtually during times when in-person enrollments are not possible presents a recruitment barrier for the study. As such, we are requesting alteration of documentation of caregiver consent, youth (7-17) assent, and young adult (18-24) consent when a virtual enrollment is to be conducted. When this occurs, the therapist will contact the client and/or caregiver ahead of time to see if they are interested in participating in the study. If the client and/or caregiver is interested, research staff will obtain verbal assent/consent via a virtual platform. As with in-person consents, assent will be obtained from youth ages 7-17, consent will be obtained from young adults age 18-24, and consent will be obtained from caregivers of clients age 7-17. If verbal assent/consent is not obtained from all necessary parties, study participation will not take place.

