Official Study Title: Increasing Accuracy and Efficiency of Fidelity Measurement in CBT

Brief Title: Project FACTS (Fidelity Accuracy: Comparing Three Strategies)

NCT02820623

May 11, 2020

Executive Summary

1. Description of theory, methodology, intent of study

Our objective is to compare the accuracy, costs, and cost-effectiveness of three fidelity measurement methods to assess fidelity to cognitive-behavioral therapy for youth. We will randomize up to 170 therapists, implementing cognitive-behavioral therapy to 3 conditions: self-report, chart stimulated recall, and behavioral rehearsal (N = about 56 for each group). To calculate our outcomes of interest, each condition will be compared to the gold-standard fidelity measurement method, direct observation.

OBJECTIVES

Objective 1: To identify the most accurate fidelity measurement method.

Objective 2: To estimate the economic costs and cost-effectiveness of the fidelity measurement methods.

Objective 3: To compare stakeholders' motivation to use each method, as well as identify their perceived barriers and facilitators to use of each method.

This study will have a significant positive impact in two ways. First, it will validate fidelity measurement methods that can then be used by implementation scientists for research. Second, it will produce tools that can be used by community mental health clinics to monitor therapist fidelity, an indicator of therapy quality.

BACKGROUND

The significance of this study is its potential to reduce the research-to-practice gap by identifying accurate and cost-effective fidelity measurement methods that both researchers and stakeholders in community mental health clinics can use to monitor fidelity of evidence-based practices. This will allow for the public health impact of evidence-based psychosocial interventions to reach its potential. Specifically, we use the exemplar treatment, cognitive-behavioral therapy (CBT), an established evidence-based practice for a wide range of child and adult psychiatric disorders, to test the three fidelity measurement methods. The proposed research is based on a framework which identifies fidelity as a key implementation outcome.

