Therapist fidelity is frequently measured due to its mediating role between implementation of evidence-based practices and client outcomes. Fidelity can also be conceptualized as an indicator of quality of care, which is a priority for many national organizations such as the Institute of Medicine. Fidelity includes adherence (how closely the components of a protocol are followed) and competence (how skillfully the components are implemented and therapist responsiveness to the child). The gold-standard fidelity measurement technique is direct observation, which is infeasible in community agencies due to lack of recording devices, time, and trained coders. Community mental health clinics sorely need methods of measuring fidelity that are accurate and cost-effective. Accurate methods refer to those with strong reliability and validity, whereas cost-effective methods refer to those that can be used with the limited resources in routine practice settings while providing benefit.

Therapists' self-report of their own fidelity is easy to administer, brief, and low-cost. However, the correspondence between self-report and independent observers is low (e.g., kappa of .22 in one

study). Leading scholars have suggested that self-report is frequently inaccurate because self-report measures typically include many terms that are unfamiliar to therapists; and because therapists are not trained in rating their own behavior (i.e., how to rate high vs. low behavior). One way to address these concerns is to ensure that the operational definitions of each item are clear and to train therapists in how to rate their own behavior. Additionally, two innovative methods from the medical literature, chart-stimulated recall and behavioral rehearsal, hold promise for fidelity measurement. Chart-stimulated recall entails a brief interview with a clinician about the care provided to a client, while allowing the clinician to review the client's file to assist recall. Behavioral rehearsal refers to a simulated interaction between a clinician and another individual around treatment delivery. Our goal is to test the accuracy, costs, and cost-effectiveness of each of these three methods in comparison to direct observation.

STUDY SAMPLE AND DATA SOURCE

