All research activities for Aims 1 and 3, including data collection and engagement with human subjects, will be conducted by members of the University of Pennsylvania research team. All Aim 2 research activities will be conducted by members of the University of Pennsylvania research team as well as by co-investigators from Temple University.

ANALYSIS PLAN

All analyses are by intent-to-treat and will occur at the University of Pennsylvania Center for Mental Health Policy and Services Research under the direction of study biostatistician, [name]. Differences across the three arms of the study will be analyzed using SAS PROC MIXED. We will conduct three mixed-effects multivariate regression models. The dependent variable is difference in score between direct observation and the specific fidelity method under consideration. We will measure the dependent variables in three ways: raw score adherence, raw score competence, and total fidelity t-score (composite of adherence and competence raw score). We will conduct two sets of analyses. In the first set, the model will include two fixed effects (fidelity measurement method and site) and a random effect for therapist to account for the nesting

of patients within therapists. Our primary interest is in the beta coefficient for the fidelity measurement method, which tells us whether there is any difference in accuracy between the intervention arms. Our first hypothesis is that both chart-stimulated recall and behavioral rehearsal (i.e., total fidelity t-score) will be more accurate than self-report. Our second hypothesis is that chart-stimulated recall will capture adherence best. Our third hypothesis is that behavioral rehearsal will capture competence best. To test these hypotheses, we will use the model described above to conduct custom contrasts in the regression models to examine whether the mean of the dependent variable differs for each pair-wise comparison of our intervention arms. We will then repeat that analysis after transforming the dependent variable into t-scores to allow computation of standardized differences for each pairwise comparison, so that we can rank accuracy. The second model will include an additional fixed-effect term for time and an interaction (time X fidelity measurement method), allowing us to examine if there are changes in outcome over time by measurement method. This is important in case there are differential practice effects across condition over time.

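### Aim 1 ranks accuracy only by the mean of a difference score, so a method that does not track observed fidelity can come first

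*Combined protocol and SAP*

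**What the plan says.** The Objectives section of the combined protocol and SAP sets "Objective 1: To identify the most accurate fidelity measurement method" and adds that the study "it will validate fidelity measurement methods that can then be used by implementation scientists for research". It also promises tools with which clinics can monitor therapists. The Background section gives the meaning of accuracy: "Accurate methods refer to those with strong reliability and validity". It motivates the trial with an agreement statistic: "the correspondence between self-report and independent observers is low (e.g., kappa of .22" in one cited study.

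The Analysis Plan section holds the only accuracy analysis. "The dependent variable is difference in score between direct observation and the specific fidelity method under consideration", and "We will measure the dependent variables in three ways: raw score adherence, raw score competence, and total fidelity t-score". In the first set of analyses, "the model will include two fixed effects (fidelity measurement method and site) and a random effect for therapist to account for the nesting"; the clustering meant is that of clients under each therapist. Custom contrasts test whether the mean of this outcome differs between each pair of arms, and a repeat on t-scores is used to rank accuracy. The second model adds time and its interaction with method. The section does not say whether the difference is signed or absolute. It plans no correlation, ICC, kappa, concordance coefficient, slope on the observed score or limits of agreement for any arm.

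**The concern.** Monitoring fidelity means telling better sessions from worse ones. The mean of a difference score does not measure that. A score that hardly varies and sits near the average observed score has a small mean difference, yet says nothing about which session was delivered well. A method that follows observation closely but reads a little high or low has a larger mean difference, although it is informative and could be recalibrated. Ranking on the mean can therefore reverse the order that the protocol's own definition of accuracy implies. Nor can the planned output show whether any arm improves on the weak agreement cited as the reason for the trial. The random therapist effect does not help: as written it is common to the arms, handles nesting, and is not an accuracy result.

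**Working it through.** The plan gives no figure to reproduce, so this is an illustration.

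**Inputs from the document.** About 56 therapists per arm (Executive Summary: up to 170 in three arms, 170/3 = 56.7) and 3 sessions per therapist (Procedures). The target of 405 clients implies a smaller arm: 405/3 = 135 therapists, 135/3 = 45 per arm.

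**Assumptions, not in the document.** Normal scores; observed-score SD of 1; within-therapist ICC 0.3 (range 0.1 to 0.5); two-sided 5% tests; and all method SDs, correlations and biases below.

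**Formulas.** For a method with SD k and correlation r with observation, the SD of the difference is s = sqrt(1 + k² − 2kr). With no bias, the mean absolute difference is 0.798 × s. The variance of a between-arm contrast is (s_A² + s_B²)(1 + 2 × ICC)/(3n).

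**Signed difference.** Method A scores every session at the observed mean: k = 0, s = 1, expected difference 0. Method B has k = 1, r = 0.9 and a bias of 0.3, so s² = 2(1 − 0.9) = 0.2. With n = 56 and ICC 0.3, the variance is 1.2 × 1.6/168 = 0.01143 and the SE is 0.107. Then 0.3/0.107 = 2.81, and power is Φ(2.81 − 1.96) = 80%.

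| Bias of B (SD) | ICC 0.3 | Range over ICC 0.1–0.5 |
|---|---|---|
| 0.2 | 46% | 39–58% |
| 0.3 | 80% | 71–90% |
| 0.5 | 99.7% | 99–100% |

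These are the chances of a significant contrast in favour of the uninformative method. The concordance correlation, 2rk/(1 + k² + bias²), reverses the order: 0 for A and, at a bias of 0.3, 1.8/2.09 = 0.86 for B.

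**Absolute difference.** The constant score has a mean of 0.80. Unbiased methods with k = 1 have:
- r = 0.22: 0.798 × sqrt(1.56) = 1.00
- r = 0.4: 0.798 × sqrt(1.20) = 0.87
- r = 0.5: 0.798 × 1 = 0.80

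So the constant score wins only below about r = 0.5. Against r = 0.9 it wins only if that method's bias exceeds about 0.78 SD.

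A compressed but not constant score (k = 0.2, r = 0.1) also has s = sqrt(1 + 0.04 − 0.04) = 1 and a mean of 0.80. Simulation with 45 therapists per arm and ICC 0.3 (4,000 trials, t-test on therapist means) gave:

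| Competitor | Compressed score has lower mean | Significantly lower |
|---|---|---|
| r = 0.22 | about 99% | about 59% |
| r = 0.4 | about 82% | about 15% |
| r = 0.6 | about 13% | about 0.1% |

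**Precision of an added agreement measure.** With ICC 0.3, the effective number of sessions per arm is 135/1.6 = 84 to 168/1.6 = 105. The 95% half-width of a session-level correlation, 1.96(1 − r²)/sqrt(n_eff), is 0.14–0.16 at r = 0.5 and 0.17–0.19 at r = 0.3. For a difference between two arms, multiply by sqrt(2): 0.20–0.23 at r = 0.5 and about 0.25–0.28 at r = 0.3.

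**The case against.** The definition of accuracy is a general sentence in the Background, not an endpoint definition. The Executive Summary says each condition will be compared with direct observation as the gold standard, and closeness to a gold standard is a recognised form of criterion validity. This stands: mean bias is one part of validity, so the planned analysis is incomplete rather than irrelevant.

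Nothing in the document suggests that any method yields near-constant scores centred on the observed mean. The Background attributes self-report error to unfamiliar terms and untrained raters. This also stands: the scenarios show what the outcome permits, not what is expected.

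Three stronger readings are tempting and fail.
- A reader might infer that the problem is equally serious whether the difference is signed or absolute. It is not. Unbiased methods tie on the signed difference, so misranking there needs a biased competitor. On the absolute difference it needs a weakly correlated or heavily biased one.
- A reader might take 82% and 99% as the chance that the trial declares the wrong winner. They are rank orders of sample means. The contrasts reach significance in only about 15% and 59%. The plan does rank, however, so order alone matters.
- A reader might infer that three sessions per therapist supply the missing reliability. They come from separate clients, each recorded once, so their similarity reflects therapist consistency, not measurement repeatability.

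The kappa of .22 is not a correlation, so r = 0.22 is only indicative.

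**Conclusion.** The point holds as a gap between the stated meaning of accuracy and the only accuracy outcome analysed. It concerns the Aim 1 models; the motivation models of Aim 3 are not affected. Followed exactly, the plan can name as most accurate a method that does not track observed fidelity.

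The size depends on the unstated form of the difference. Signed, which is the literal reading, the contrast sees only bias and errors in opposite directions cancel. Two arms with equal and opposite biases would even differ significantly while being equally inaccurate. Absolute, the harm is largely confined to choosing between an uninformative method and a weak or heavily biased one. Every SD, correlation, bias and ICC behind the percentages is assumed. The document does not support the claim that the ranking will be wrong, only that the planned outcome cannot guard against it.

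**What to change.** Keep the difference-score models and amend the Analysis Plan section as follows.

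1. State that the outcome is the absolute difference, and report signed bias by arm separately.
2. For adherence, competence and total fidelity, report by arm a session-level absolute-agreement ICC or concordance correlation with direct observation, and the slope of method score on observed score. Give 95% intervals that allow for clustering by therapist, and the between-arm differences.
3. Place these results beside the difference-score ranking, and do not call a method most accurate or validated on the mean difference alone.

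The cost is a paragraph and some programming. Each included session should already yield a method score and an observed score, so no extra coders, sessions or participants are needed. Measurement reliability in the repeat-measurement sense would remain unaddressed, and the report should say so.

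There are three downsides. Between-arm differences in agreement will have 95% half-widths of about 0.20–0.23 when the correlations are near 0.5, and wider when they are lower. Agreement coefficients depend on the spread of fidelity among each arm's therapists. The two rankings may also differ, in which case both must be reported as they stand; neither should overrule the other automatically.
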